6.3 Visit 01 (Week 2) Day 14±5

The following procedures will be performed during this visit (this visit may take about 2 hours):

- Assess the Subject for possible AEs and Concomitant Medication use.
- Review amount of study drug returned and assess compliance.
- Review the use of the eDiary and encourage the Subject and Study Partner to make and upload entries two times per day.
- Perform orthostatic vital sign measurements: blood pressure (systolic and diastolic) and heart rate (beats/minute).
- Record the Subject's body temperature (°C).
- Perform a resting 12-Lead EKG.
- Perform clinical assessment for suicidal ideation with the CSSRS.
- Collect blood samples for routine hematology/serum chemistry (refer to Section 6.13.5 for required tests).
- If two tubes not collected at Baseline Visit (Day 0), collect blood samples for CAGn genotyping and/or DNA storage (refer to University of Rochester Medical Center Lab Manual for sample handling and processing requirements).
- Collect urine for routine urinalysis (refer to Section 6.13.5 for required tests).

- Dispense study drug and instruct the Subject and Study Partner about correct administration of study drug (i.e., change in dose to 120 mg BID SRX246 or Placebo).
- Instruct Subject and Study Partner to bring unused study drug to each study visit, and to immediately report any AEs to the Investigator or Coordinator.

6.4 Visit T1 (Week 4) Day 28±5

This visit will be a Telephone follow-up to perform the following (this may take about 15 minutes):

- Assess the Subject for possible AEs and Concomitant Medication use.
- Inquire about study drug compliance - assess whether study drug is being taken properly by the Subject (and if applicable, Study Partner) self-report. Subjects who do not experience intolerance will remain on their daily dose of study drug.
- Instruct Subject and Study Partner to bring unused study drug to each study visit, and to immediately report any AEs to the Investigator or Coordinator.
- Review the use of the eDiary and encourage the Subject and Study Partner to make and upload entries two times per day.

6.5 Visit 02 (Week 6) Day 42±5

The following procedures will be performed during this visit (this visit may take about 3 hours):

- Assess the Subject for possible AEs and Concomitant Medication use.
- Review amount of study drug returned and assess compliance.
- Review the use of the eDiary and encourage the Subject and Study Partner to make and upload entries two times per day.
- Perform orthostatic vital sign measurements: blood pressure (systolic and diastolic) and heart rate (beats/minute).
- Record the Subject's weight (kg) and obtain body temperature (°C).
- Perform a resting 12-Lead EKG.
- Collect blood samples for routine hematology/serum chemistry, and for a serum pregnancy test for women of childbearing potential (refer to Section 6.13.5 for required tests).
- If two tubes not collected at Baseline Visit (Day 0), collect blood samples for CAGn genotyping and/or DNA storage (refer to University of Rochester Medical Center Lab Manual for sample handling and processing requirements).
- Collect urine for routine urinalysis (refer to Section 6.13.5 for required tests).
- Perform clinical assessment for suicidal ideation with the CSSRS (Since Last Visit).
- Conduct UHDRS assessment (Huntington Study Group 1999).
- Total Functional Capacity (TFC) score must be between 5-13, inclusive.
 - TFC is <7, an assessment of capacity to consent will be required.
- Assess the Subject using the Clinical Global Impression – Improvement (CGI-I).
- Administer the Problem Behaviors Assessment short form (PBA-s) to the Subject and Study Partner, together.
- Administer the Aberrant Behavior Checklist (ABC), irritability subscale to the Study Partner.
- Administer the Cohen-Mansfield Agitation Inventory (CMAI) to the Study Partner.
- Administer the HD Irritability Scale (IS) to the Subject and Study Partner, separately.
- Administer the HD QoL to the Subject and Study Partner, together.

- Administer the Caregiver Burden Questionnaire to the Study Partner.
- Dispense study drug and instruct the Subject and Study Partner about correct administration of study drug (i.e., either remaining at 120 mg BID SRX246 or Placebo, change in dose to 160 mg BID SRX246 or Placebo, or possible dose reduction based on intolerance).
- Instruct Subject and Study Partner to bring unused study drug to each study visit, and to immediately report any AEs to the Investigator or Coordinator.
- At the time of scheduling the next visit, remind the Subject not to take drug (or placebo) on the morning of the next visit, that the study drug will be taken in the clinic during the next visit to enable sparse PK sampling.

6.6 Visit 03 (Week 8) Day 56±5

The following procedures will be performed during this visit (this visit may take about 4 hours):

- Assess the Subject for possible AEs and Concomitant Medication use.
- Review amount of study drug returned and assess compliance.
- Review the use of the eDiary and encourage the Subject and Study Partner to make and upload entries two times per day.
- Perform orthostatic vital sign measurements: blood pressure (systolic and diastolic) and heart rate (beats/minute).
- Record the Subject's body temperature (°C).
- Perform a resting 12-Lead EKG.
- Collect blood samples for routine hematology/serum chemistry (refer to Section 6.13.5 for required tests).
- If two tubes not collected at Baseline Visit (Day 0), collect blood samples for CAGn genotyping and/or DNA storage (refer to University of Rochester Medical Center Lab Manual for sample handling and processing requirements).
- Collect urine for routine urinalysis (refer to Section 6.13.5 for required tests).
- Prepare the subject for PK blood sampling for the sparse PK study. Subjects will have been prompted to note the time at which the dose of study compound was taken the night before (either in their eDiaries or on a piece of paper), and to bring their dose for the morning of the visit with them but not to take it until they are instructed to do so.
 - Blood will be drawn as soon as the patient arrives in the clinic; then the morning dose of drug should be given and the time recorded.
 - Perform orthostatic vital sign measurements: blood pressure (systolic and diastolic) and heart rate (beats/minute) approximately 1-2 hours after taking the morning dose (estimated time to Cmax).
 - Two (2) hours later (time to be recorded), blood will be drawn again.
 - Process the PK samples as directed in the University of Rochester Medical Center Lab Manual
- Dispense study drug and instruct the Subject and Study Partner about correct administration of study drug (i.e., either 120 mg BID SRX246, 160 mg BID SRX246 or Placebo, or possible dose reduction based on intolerance).
- Instruct Subject and Study Partner to bring unused study drug to each visit, and to immediately report any AEs to the Investigator or Coordinator.

- If not performed during this Visit, at the time of scheduling the next visit, remind the Subject not to take drug (or placebo) on the morning of the next visit, that the study drug will be taken in the clinic during the next visit to enable sparse PK sampling.

6.7 Visit 04 (Week 10) Day 70±5

The following procedures will be performed during this visit (this visit may take about 2 hours, if PK required this visit may take about 3 hours):

- Assess the Subject for possible AEs and Concomitant Medication use.
- Review amount of study drug returned and assess compliance.
- Review the use of the eDiary and encourage the Subject and Study Partner to make and upload entries two times per day.
- Perform orthostatic vital sign measurements: blood pressure (systolic and diastolic) and heart rate (beats/minute).
- Record the Subject's obtain body temperature (°C).
- Perform a resting 12-Lead EKG.
- Collect blood samples for routine hematology/serum chemistry (refer to Section 6.13.5 for required tests).
- If two tubes not collected at Baseline Visit (Day 0), collect blood samples for CAGn genotyping and/or DNA storage (refer to University of Rochester Medical Center Lab Manual for sample handling and processing requirements).
- Collect urine for routine urinalysis (refer to Section 6.13.5 for required tests).
- If not performed during Visit 03, prepare the subject for PK blood sampling for the sparse PK study.
- Dispense study drug and instruct the Subject and Study Partner about correct administration of study drug (i.e., either 120 mg BID SRX246, 160 mg BID SRX246 or Placebo, or possible dose reduction based on intolerance).
- Instruct Subject and Study Partner to bring unused study drug to each visit, and to immediately report any AEs to the Investigator or Coordinator.

6.8 Visit 05 (Week 12) Day 84±5

The following procedures will be performed during this visit (this visit may take about 4 hours):

- Assess the Subject for possible AEs and Concomitant Medication use.
- Retrieve all supplies of the study drug, review amount of study drug returned and assess compliance.
- Retrieve the eDiary and ensure all data have been transmitted.
- Perform a Complete Physical Examination, including neurological.
- Perform orthostatic vital sign measurements: blood pressure (systolic and diastolic) and heart rate (beats/minute).
- Record the Subject's weight (kg) and obtain body temperature (°C).
- Perform a resting 12-Lead EKG.
- Collect blood samples for routine hematology/serum chemistry, and for a serum pregnancy test for women of childbearing potential (refer to Section 6.13.5 for required tests).
- Collect blood samples for CAGn genotyping and/or DNA storage if both not collected at Baseline (refer to University of Rochester Medical Center Lab Manual for sample handling and processing requirements).

- Collect urine for routine urinalysis (refer to Section 6.13.5 for required tests).
- Perform clinical assessment for suicidal ideation with the CSSRS (Since Last Visit).
- Conduct UHDRS assessment (Huntington Study Group 1999).
- Total Functional Capacity (TFC) score must be between 5-13, inclusive.
 - If TFC is <7 an assessment of capacity to consent will be required.
- Assess the Subject using the Clinical Global Impression – Improvement (CGI-I).
- Administer the Problem Behaviors Assessment short form (PBA-s) to the Subject and Study Partner, together.
- Administer the Aberrant Behavior Checklist (ABC), irritability subscale to the Study Partner.
- Administer the Cohen-Mansfield Agitation Inventory (CMAI) to the Study Partner.
- Administer the HD Irritability Scale (IS) to the Subject and Study Partner, separately.
- Administer the HD QoL to the Subject and Study Partner, together.
- Administer the Caregiver Burden Questionnaire to the Study Partner.
- Upon confirmation that the Subject is medically stable and all study procedures have been completed, discharge the Subject from the visit and instruct the Subject and Study Partner to immediately report any AEs to the Investigator or Coordinator.

6.9 Visit T2 (Follow-Up) Day 91±5

This visit will be a Telephone follow-up to perform the following (this may take about 15 minutes):

- Assess the Subject for possible AEs and Concomitant Medication use.
- Upon confirmation that the Subject is medically stable and all study procedures have been completed, discharge the Subject from the study.

6.10 Unscheduled Visits or Telephone Contacts (Visit UXX or TXX)

An unscheduled visit (UXX) or telephone contact (TXX) may be performed at any time during the study at the Subject's or Study Partner's request or as deemed necessary by the site Investigator. The date and reason for the UXX or TXX, as well as the results of any additional testing, will be recorded in the source documentation. Reasons may include, but are not limited to, the need to repeat a suspect laboratory safety test, a potential severe side effect, worsening of behavioral symptoms, multiple missed doses of medication.

6.11 Premature Withdrawal (PW)

Subjects have the right to withdraw from the study at any time without prejudice. The site Investigator may withdraw study drug from a Subject in the study in the event of intercurrent illness, adverse events, other reasons concerning the health or well-being of the Subject, or in the case of lack of cooperation, non-compliance, protocol violation or other administrative reasons. Premature withdrawal will be implemented in the case of emergency disclosure of drug treatment (i.e., unblinding).

A Subject may withdraw or be withdrawn from the study for the following reasons:

Administrative

1. Withdrawal of consent
2. Request of [Sponsor or Principal Investigator]

3. Request of primary care physician
4. Non-compliance
5. Failure to meet entry criteria
6. Pregnancy
7. Protocol deviation
8. Subject deemed lost to follow up/failure to return
9. Early termination of study
10. Other

Adverse Event

1. Worsening of the disease under study
2. Worsening of pre-existing disease (other than disease under study)
3. Intercurrent illness
4. Death
5. Major/clinically significant alteration in laboratory values after beginning study drug
6. Other adverse event

In the event of premature withdrawal from the study, every effort should be made to obtain an in-person final visit, which should include the same procedures as Visit 05 (Week 12). This can be performed whether or not the withdrawal is determined at a regularly scheduled study visit or at an unscheduled visit. Visit T2 should still be performed 7±5 days after the final in-person visit.

Should a scheduled in-person visit be impossible, conduct as many of the verbal assessments as possible, with special emphasis on obtaining information on possible AEs, and arrange for return of study drug.

Reasons for withdrawal of the Subject prior to completion of the study must be stated in the CRF and in the site source documentation for all study Subjects who were enrolled in the study. The CCC and the IMM must be informed within 24 hours of all study Subjects who are withdrawn due to an adverse event.

6.12 Dosage Adjustments

Dosage adjustments (dose reductions and suspensions) will be allowed if warranted, in the clinical judgment of the site Investigator in consultation with the medical monitor. Restarting study drug after suspensions will be allowed. The overall goal is to encourage each Subject to reach the target dosage and complete the study. The CTCAE Version 4.0 may be used as a reference guide for dosage adjustments. Grade 2 or greater adverse effects for laboratory values and clinical events should be considered when evaluating tolerability and determining whether a dose reduction is warranted. While these criteria will be used as a guide, site investigators, in consultation with the medical monitor, will ultimately make the decisions about dosage adjustments.

6.12.1 Dosage Reduction

Dosage reductions are permitted during the study due to tolerability issues or adverse events that are thought to be related to study drug. In the first two weeks of the trial, subjects who cannot tolerate the drug will receive no more capsules but will be encouraged to continue participating in the study. Reductions can be performed once between study weeks 2 and 6, and twice between study weeks 6 and 12. The project manager should be notified in this case to discuss and confer with the protocol PI and/or medical monitor if necessary. A dosage reduction is accomplished by lowering the total daily dose (as deemed necessary by the site Investigator) until symptoms resolve or reduced dosage is tolerated by the Subject. Dose reduction can only be performed up to a maximum of 2 times, until the Subject is removed from further dosing with study drug.

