6.12.2 Dosage Suspension

Administration of the study drug may be interrupted for intolerable adverse effects thought to be related to study drug, intercurrent illnesses, or surgery at any time during the study. These situations will be handled on a case-by-case basis in consultation with the protocol PI or medical monitor. A suspension may last up to one week. Subjects will be removed from the study if a suspension is predicted to last longer than one week (e.g., a scheduled surgery with long recovery period or a severe illness such as a stroke that is unlikely to resolve in less than one week). Study drug suspensions for planned travel, holidays, or vacations of the Subject (or Study Partner) are to be avoided.

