6.12.3 Premature Drug Discontinuation

There is no downward titration necessary when the study drug is permanently discontinued. If a Subject cannot tolerate the dosing regimen, study drug will be permanently discontinued.

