7 MANAGEMENT OF ADVERSE EXPERIENCES

The following types of events were reported in Subjects taking SRX246 in Phase I studies: tachycardia, conjunctival hyperemia, upper abdominal pain, diarrhea, epigastric discomfort, gastroesophageal reflux, lip pain, nausea, vomiting, chest pain. Almost all of these were mild in intensity, and they were not dose related. Thus, at this point, there are no expected adverse events or special precautions that need to be given to trial Subjects.

Section 10 below also includes a detailed description of AE definitions, assessment/detection, grading (severity), potential relatedness to the investigational product, and reporting requirements. Below is a general strategy to guide modification or discontinuation of the study drug in response to AEs. The decision to decrease the dose of SRX246 or discontinue it altogether should be made by the site PI in consultation with the medical monitor should factor in potential relatedness of the AE to the study drug.

AE Grade	Management
≤ Grade 1 (mild)	No change in dose
Grade 2 (moderate)	*Hold until ≤ Grade 2. Resume at same dose level.
Grade 3 (severe)	*Hold until ≤ Grade 2. Resume at one dose level lower**
Grade 4 (life threatening or disabling)	Off protocol therapy

*Patients requiring a delay of > 1 week should go off therapy. Subjects can only hold medication once throughout the study. A Subject requiring a second hold should go off therapy.

**Patients requiring > two dose reductions should go off therapy.

Grade 1 AEs are defined as signs or symptoms that are easily tolerated. Grade 2 AEs are intense enough to interfere with usual activities. Grade 3 AEs interfere significantly with a Subject's ability to do work or his/her usual activities.

Worsening of Irritability and other Behavioral Symptoms

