8 GENERAL DESIGN ISSUES

The study design consists of three parallel arms: placebo and two final doses of SRX246 (120 mg BID and 160 mg BID). Thirty-six patients will be randomized into each study arm. Since we have only given SRX246 to generally healthy subjects thus far, and since some HD patients may be frailer population, we have elected to initiate treatment at 80 mg BID; to increase the dose of drug to 120 mg BID after two weeks in those patients who have tolerated the starting dose; and to increase the dose of drug again after 2 additional weeks in those patients who are taking 160 mg BID. Subjects in the placebo group will take capsules that will be identical in appearance to those containing SRX246. Thus, patients and study staff will both be blind to treatment, and twice as many Subjects will receive active agent as placebo. The placebo group will be used for comparison with each active drug group.

Subjects who are unable to increase their dose of drug can remain in the study at the highest dose they can tolerate, and Subjects who find the drug intolerable can reduce the dose of drug (to 80 mg BID of SRX246 or placebo, but no lower without dropping out of the study). The goal is to study the behavioral scales in as many people as possible because we feel that this will be important to the clinical research community.

At the end of the trial, data from all Subjects who were given placebo will be combined, and two pairwise tests will be performed (120 mg vs placebo, 160 mg vs placebo--see below).

It may be necessary to screen as many as 150 candidates to enroll 108 Subjects. Up to 20 NeuroNEXT sites may participate in the study, with each site's goal to enroll about 5-6 Subjects within the first 18 months of the trial.

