2. PRIMARY ENDPOINT

The primary endpoint for tolerability is defined as the proportion (percentage) of study participants who completed the study while active on their assigned intervention arm. Study completion can occur despite temporary drug interruptions, protocol deviations, etc. Conversely, a non-completer is a study participant who withdraws from study drug (either participant-initiated or researcher-initiated) prior to the normal study termination as described in the protocol or who completes the study on a dose below their assigned dose.

Each treatment group will be compared to the placebo group, and the statistical test of equivalence of tolerability will involve two pairwise tests (120 mg vs. placebo, 160 mg vs. placebo).

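### For a transient intolerable adverse event in weeks 0-2, Protocol 6.12.1 ends dosing while 6.12.2 and section 7 (Grade 2) allow hold and restart, and the choice can change a participant's primary-endpoint score

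*Protocol*

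**What the plan says.** Four parts of the protocol speak to a participant who has an intolerable, drug-related event while on the starting dose.

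- **6.12.1 (Dosage Reduction):** "In the first two weeks of the trial, subjects who cannot tolerate the drug will receive no more capsules". Such participants are encouraged to stay in the study off drug.
- **6.12.2 (Dosage Suspension):** dosing "may be interrupted for intolerable adverse effects thought to be related to study drug, intercurrent illnesses, or surgery at any time during the study". It adds: "A suspension may last up to one week". Section 6.12 permits restart after a suspension.
- **6.12.3 (Premature Drug Discontinuation):** "If a Subject cannot tolerate the dosing regimen, study drug will be permanently discontinued". Under 6.12.4, restart after discontinuation is open only when the reason was unrelated to safety.
- **Section 7:** Grade 2 events are held and resumed at the same dose. For Grade 3, after a hold: "Resume at one dose level lower". Grade 4 goes off therapy. The table has no exception for weeks 0-2.

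Section 8 adds: "Subjects who find the drug intolerable can reduce the dose of drug". It sets 80 mg BID as the floor for anyone staying on treatment, and that is also the dose in weeks 0-2.

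SAP section 2 defines the primary endpoint. "Study completion can occur despite temporary drug interruptions, protocol deviations, etc". A participant who withdraws from study drug early, whoever initiates it, is a non-completer. So is one who finishes below the assigned dose.

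**The concern.** Section 6.12.1 is worded as mandatory and 6.12.2 as permissive, but both cover a participant with an intolerable related event in week 1. One ends dosing; the other allows a short hold and a return to drug. No sentence says which comes first, or that 6.12.1 applies only once a hold has failed.

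This matters because the completer proportion is the Go/No-Go endpoint for each dose (SAP section 7). If similar events are handled under different sections, part of that proportion reflects the section applied and not the tolerability of the drug.

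**Working it through.** **1. One participant under each rule.** Take an intolerable, related event in week 1 that settles within a week.

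| Rule applied | Action | Score under SAP section 2 |
|---|---|---|
| 6.12.1 | Dosing ends; 6.12.4 gives no route back, since the reason is safety | Non-completer |
| 6.12.2 with 6.12 | Hold, then restart | Completer if the assigned dose is taken to the end |
| Section 7, Grade 2 | Hold, resume at same dose | Completer on the same condition |
| Section 7, Grade 3 | Hold, resume one level lower | Cannot be carried out: nothing below 80 mg BID |
| Section 7, Grade 4 | Off therapy | Non-completer, as in 6.12.1 |

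Within section 7, the opposite score is therefore confined to Grade 2.

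**2. Reproduce the planned sample size.** Inputs from Protocol 8.2 and SAP section 9: placebo 0.80, active 0.60, margin 0.50, one-sided alpha 0.025, power 80%.

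n = (z₀.₉₇₅ + z₀.₈₀)² × [π_P(1−π_P) + π_T(1−π_T)] / [δ − (π_P − π_T)]²

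= (1.960 + 0.842)² × (0.16 + 0.24) / 0.30² = 34.88, rounded up to 35.

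This matches the protocol's 35 and is close to the SAP's 36. By the same formula, power is 80.1% with 35 per arm and 81.2% with 36.

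**3. Effect of reclassification.** Let f be the share of the active arm who would be completers if held and restarted but are non-completers if stopped. With 36 per arm, one participant is 1/36 = 2.8 points; f = 5% is 1.8 participants and f = 10% is 3.6. The documents give no value for f, so 5% and 10% are assumptions. Placebo is left unchanged and all cases move one way.

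P(Go) = Σ Σ Bin(x; 36, π_P) × Bin(y; 36, π_T − f), summed over the pairs (x, y) that reject.

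The rejection region comes from an exact unconditional test with score ordering, standing in for the SAP's exact interval (attained size 0.0249).

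| Placebo/active before shift | f = 0 | f = 5% | f = 10% |
|---|---|---|---|
| 0.80/0.60 (planning bound) | 0.838 | 0.680 | 0.486 |
| 0.91/0.83 (Table 4 means) | 0.999 | 0.987 | 0.943 |

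The Table 4 means are the protocol's own: placebo 0.91, mean difference 0.08. Losses are 16 and 35 points in the first row, 1 and 6 in the second. The normal formula agrees in pattern: 81.2%, 65.2% and 46.6% at the planning bound; 99.3% and 95.3% after the two shifts at the Table 4 means.

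**4. Where a single case decides.** In the same test, with 29 placebo completers Go needs at least 19 active completers (p = 0.015; 18 gives 0.033). With 33 placebo completers it needs 22 (p = 0.024; 21 gives 0.042). One reclassified participant changes the decision only at these cut-offs.

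**The case against.** The sections can be read in sequence. Section 6.12.1 concerns reduction, and its weeks 0-2 sentence may only say what happens when no lower dose exists. Section 6.12.3 may mean a regimen not tolerated even after the permitted reductions. Both readings are reasonable, but neither is written down. The second is enough to stop 6.12.3 being counted as a separate firm contradiction.

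Section 6.12 leaves dosing decisions to the investigator with the medical monitor, 6.12.2 handles suspensions case by case, section 7 presents its table as guidance, and 10.3.4 makes suspensions, reductions and early discontinuations reportable within 24 hours. This narrows variation between sites. It does not remove it, because the monitor has no stated order of precedence to apply.

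Early cases may be few. The single-dose study had no discontinuations, and the 14-day study had none due to adverse events at up to 120 mg BID. Those were small healthy-volunteer studies, and section 8 gives possible frailty in HD as the reason for starting at 80 mg BID. They suggest a low rate but do not establish one.

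A reader might infer that the section followed always decides completer status. It does not: Grade 4 agrees with 6.12.1, Grade 3 has no executable resume step, and a restarted participant must still finish on the assigned dose. A reader might also start from placebo 0.90 and active 0.65, where P(Go) falls from 0.766 to 0.569 and 0.357, losses of 20 and 41 points. Those scenarios have differences of 0.25 to 0.35, beyond the plan's 0.20 bound and the largest Table 4 difference of 0.18.

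**Conclusion.** The inconsistency is real and reaches the primary endpoint, but for a limited group: participants with an intolerable, related, transient event in weeks 0-2 who would otherwise finish on the assigned dose. For them, 6.12.1 gives a non-completer and hold-and-restart gives a completer. Separately, section 7's Grade 3 instruction cannot be followed in that period.

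The effect on the Go decision depends on an unstated rate of such events. It is material near the planning bound and small at the Table 4 means, where the 0.50 margin absorbs most of it. Both illustrations shift only the active arm, all in one direction, although the rules are applied blind and reach placebo participants too. They therefore show sensitivity and are not a forecast. The completer consequence rests on the SAP definition; Protocol 8.1.1 does not define the term.

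**What to change.** Reconcile 6.12.1, 6.12.2, 6.12.3 and the section 7 table so that one stated rule governs weeks 0-2, with section 7 referring to it. Which rule that should be is a clinical decision on which this point takes no view. SAP section 2 already assigns interruption, withdrawal and reduced final dose to completer or non-completer, and can stand.

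Add one sensitivity analysis to the SAP: list weeks 0-2 intolerance cases by arm with the action taken, and repeat the primary test with those cases scored the other way. Scoring a stopped participant as a completer is a bound, since nobody knows whether that person would have finished on the assigned dose. The SAP describes randomization in the past tense, so if the clarification comes too late to affect conduct, this analysis remains useful; 10.3.4 already requires the relevant actions to be reported.

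Cost: a clarification memo, a short SAP addition and one extra analysis run. No added participants or procedures.
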